7.1.1 Subsequent Boluses

In both arms of the trial: if a SBP of \geq 90 mmHg or a radial pulse returns after the administration of a bolus and remains present, no further fluid will be administered. If a SBP of \geq 90 mmHg or the radial pulse does not return or if it is subsequently lost, further boluses will be administered until it is restored. In each case a maximum of 4 boluses can be administered as part of the trial interventions.

Any additional fluid boluses required to maintain blood pressure after administration of the 4 trial boluses should be given according to standard local practice.

7.1.2 Lactate Concentration

In cases where the participant is still on scene 2 hours after randomisation, a second capillary blood test should be taken to measure lactate concentration using a point-of-care lactate device at 2 hours after randomisation.

7.2 On Arrival at the Receiving Hospital ED

Trial data collected by the PHEM team will be shared with the RHS, in accordance with local policy and recorded on the RePHILL PHEM CRF.

7.2.1 Vital Signs

The following will be measured:

- Heart rate measured in beats per minute (bpm)
- Blood pressure measured in mmHg
- Respiratory rate is the number of breaths (inhalation exhalation cycles) counted in one minute
- Capillary oxygen saturation (SpO₂) measured by application of a probe to a finger, toe or ear. SpO₂ is the percentage of haemoglobin that is oxygenated

7.2.2 Tissue Oxygenation and Perfusion

Selected sites only

When possible, Near-infra-red spectroscopy (NIRS) will be used to monitor tissue oxygenation and perfusion via a non-invasive adhesive pad attached to the participant's skin.

7.2.3 (Venous) Lactate Concentration

Lactate concentration will be measured on arrival at ED and 2 hours after arrival as part of standard care. It will also be measured 2 hours after randomisation (if not previously done on scene), for trial purposes. Where possible, a venous sample should be taken, however if this is not possible then an arterial sample is permitted. Lactate concentration will be measured on a near-patient blood gas analyser. There is no processing required before analysis. This is drawn as a normal part of trauma care (i.e. is no extra burden for the participant). The blood volume drawn

varies between syringes but is typically between 1 mL and 3 mL, to be drawn into a preheparinised syringe.

7.2.4 Calculating Lactate Clearance

Lactate clearance[33] is expressed as a percentage per hour (%/h) and is calculated from the measurement of (venous) lactate concentration (with automated analysers that are near-patient) by the PHEM team immediately prior to randomisation (Lac₀) and at 2 hours after randomisation (Lac_h) as:

Lactate Clearance = $100 \times (Lac_0 - Lac_h)$ Lac_0 x Interval

7.2.5 Blood Samples on Admission

- Routine laboratory testing to include Full Blood Count (FBC), urea and electrolytes (U&Es) and bilirubin, coagulation and transfusion. Other tests to be included as clinically indicated
- The standard laboratory tests of coagulation are Clauss fibrinogen, prothrombin time (PT), activated partial thromboplastin time (aPTT), International Normalised Ratio (INR). INR is a ratio of PT to normal, corrected for local processes and reagents, allowing valid comparison between different laboratories
- Transfusion testing to include ABO and RhD group with assessment for mixed field group, antibody screen and Direct Antiglobulin Test (DAT)

7.2.6 Blood Sampling for ROTEM®

Selected sites only

Coagulation will be measured viscoelastically by rotational thromboelastometery (ROTEM®):

- For sites using the ROTEM[®] machine, 4.5 mL of venous blood is to be drawn into a citrated container (BD Vacutainer 367691 or equivalent). The citrated container contains the additive sodium citrate which inhibits blood clotting. This is a standard tube for blood clotting tests. No pre-processing is required.
- EXTEM and FIBTEM tests will be performed.

7.2.7 Blood Sampling for Platelet Function

Selected sites only

Selected sites will have a platelet function analyser (MultiPlate)³⁴. Three MultiPlate tests (using ADP, ASPI and TRAP agonists) will be carried out from a venous blood sample drawn into a 3 evacuated hirudin-coated blood tube (Sarstedt AG & Co. S-Monovette® 04.1944.001 or equivalent).

7.2.8 Blood Sampling for Future Research

Queen Elizabeth Hospital, Birmingham only

In anticipation of future studies, blood will be drawn for serum preparation and storage. A blood sample (1 x 5 mL) will be drawn into a pre-evacuated tube containing clot activator (BD Vacutainer 367986 or equivalent).

7.3 During Hospital Admission

The following assessments are to be made during the hospital admission as indicated by the participant's clinical condition, up to withdrawal, acute care discharge, death or day 30, whichever is earlier.

7.3.1 Acute Respiratory Distress Syndrome (ARDS)

This will be assessed at day 7. The Berlin definition of ARDS will be used for assessing participants[34]. Criteria for the diagnosis are shown in Table 1.

Table 1: Criteria for diagnosis of ARDS	
---	--

Timing	Within 1 week of a known clinical insult or new or worsening respiratory symptoms
Chest	Bilateral opacities not fully explained by effusions, lobar/lung collapse or
imaging	nodules
Origin	Respiratory failure not fully explained by cardiac failure or fluid overload
Oxygenation	$PaO_2/FiO_2 \le 40$ kPa with either PEEP or CPAP ≥ 5 cm H_2O (invasive or non-invasive)

7.3.2 Sequential Organ Failure Assessment score (SOFA) score

The extent of a participant's organ dysfunction will be recorded using the SOFA score[31]. The score is based on six components, one each for the following systems:

Respiratory

Neurological

- Cardiovascular
- Liver
- Coagulation
- Renal

The scores are assigned as shown in Tables 2 a-f.

The SOFA score will be determined daily for the duration of intensive care stay up to day 30. Scores will be derived from routine clinical and laboratory records.

Version 2.0, 16th January 2017

RePHILL Trial Protocol

Tables 2a-f: SOFA Score

Respiratory	(a)
PaO₂/FiO₂ (kPa)	Score
≥53.3	0
<53.3	1
<40.0	2
<26.7 and mechanically ventilated	3
<13.3 and mechanically ventilated	4

Neurological	(b)
Glasgow Coma Scale (GCS)	Score
15	0
13-14	1
10-12	2
6-9	3
<6	4

Cardiovascular	(C)			
Mean Arterial Pressure or inotrope requirement	Score			
MAP ≥70 mmHg	0			
MAP <70 mmHg	1			
dop ≤5 or dob (any dose)	2			
dop >5 OR epi ≤0.1 OR nor ≤0.1	3			
dop >15 OR epi>0.1 OR nor >0.1	4			
Key: dop: Dopamine, dob: dobutamine, epi: adrenaline, nor: noradrenaline Doses in μg/kg/min				

(d)
Score
0
1
2
3
4

Coagulation	(e)
Platelets×10 ³ /µl	Score
≥150	0
<150	1
<100	2
<50	3
<20	4

Renal	(f)
Creatinine (µmol/L) or urine o/p	Score
≤109	0
110-170	1
171-299	2
300-440 (or <500 mL/day)	3
> 440 (or <200 mL/day)	4

7.4 Schedule of Assessments

Refer to Table 3 below:

Table 3: Table of Assessments

	On-scene	ED arrival	2 hours post- randomisation	2 hours post- ED arrival	6 hours post- ED arrival	12 hours post- ED arrival	24 hours post- ED arrival	During hospital stay (up to day 30)
Vital signs	~	~		√	✓	✓	√	
Confirm eligibility	~							
¹ Lactate concentration	4	V	√	~				
Administer allocated treatment	✓							
Legal Representative Consent		~						
Participant Consent								✓
² Blood sampling		1		~	~			~
ROTEM [®] (participating sites only)		~						
Blood sampling (platelet function)		~						
Record fluids administered	~	~		1	✓	✓	✓	
Record surgical procedures				1	~	✓	4	
SOFA and ARDS								✓
Adverse Events	~	✓	✓	~	~	~	~	✓
³ Date and time of death of non-survivors	~	4	~	~	~	✓	1	4
⁴ Acute care discharge date								✓

¹ Capillary lactate concentrations taken on-scene will be measured using a simple point-of-care tester.

Standard laboratory tests should include a full blood count and coagulation tests. The normal sampling and laboratory practices of the site should be followed.

³ Mortality may extend beyond 30 days as it includes episode mortality

⁴ Acute care discharge date should be recorded following discharge from acute care. This may extend beyond 30 days.
8. Trial Intervention/Investigational Medicinal Products

8.1 Trial Treatments

8.1.1 PHBP Arm (Lyophilised Plasma LyoPlas N-w (LyoPlas) and PRBC)

LyoPlas is a freeze dried plasma product derived from a single donation and is licenced for use in the same indication as fresh frozen plasma. LyoPlas is licensed for use in Germany as a medicinal product under the Marketing Authorisation Number PEI.H.03075.01.1, and therefore is being classified as an Investigational Medicinal Product (IMP) in the **RePHILL** trial.

PRBC are a concentrated preparation of red blood cells that is obtained from whole blood by removing the plasma (as by centrifugation).

The PRBC used in **RePHILL** will be blood group O, RhD negative, Kell negative from NHS Blood and Transplant national stocks supplied by the blood banks that are supporting this trial.

8.1.2 Crystalloid Arm

The crystalloid resuscitation comparator arm will consist of 0.9% sodium chloride (normal saline; a solution of sodium chloride in water). This is classified as the comparator IMP in the **RePHILL** trial.

8.2 Supply of Trial Stocks and Storage Conditions

8.2.1 Trial Supplies

LyoPlas

The trial stock of LyoPlas will be shipped from the central IMP distribution centre to local receiving site pharmacies. One packaged unit of LyoPlas will comprise:

- 1 glass bottle of 200 mL freeze dried human plasma
- 1 plastic bag containing 200 mL water for injection
- 1 transfer set

PRBC

The PRBC will be from national stocks supplied by the blood banks that are supporting the **RePHILL** trial.

Normal saline

Normal saline will be from routine NHS stock and does not require any special storage conditions.

8.2.2 Packaging and Labelling of the IMPs

LyoPlas: The central IMP distribution centre will package and label the LyoPlas prior to sending out to local site pharmacies.

Normal saline: Will be provided from local site pharmacies as standard NHS stock and will be labelled by site pharmacies prior to transfer to blood banks.

Both IMPs will be labelled in compliance with the applicable regulatory requirements.

8.2.3 Storage

LyoPlas is stable between $2^{\circ}C - 25^{\circ}C$ and should be maintained within these limits whilst stored in local pharmacies and blood banks.

For the **RePHILL** trial, once packaged into the trial intervention transport boxes, the LyoPlas should be maintained between 15°C and 25°C to permit ease of preparation and administration.

PRBC is to be maintained at 4° C (± 2° C) in accordance with blood bank standard procedures. Normal saline should be stored in accordance with the Summary of Product Characteristics (SmPC).

8.3 Administration of Treatment

With respect to the interventions:

- LyoPlas may be administered via either an intravenous (IV) or intraosseous (IO) route after reconstitution in water, in accordance with the manufacturer's instructions.
- PRBC may be administered via either an intravenous (IV) or intraosseous (IO) route, according to standard clinical practice
- Normal saline may be administered via either an intravenous (IV) or intraosseous (IO) route, according to standard clinical practice

Fluid boluses should be administered according to standard practice which will usually require that they are delivered through a fluid warmer.

8.4 Interactions or Contraindications

LyoPlas and PRBC have been prepared with citrate, therefore solutions containing calcium must not be administered concurrently through the same line. Medicinal products should not be added to LyoPlas or PRBC. If an acute transfusion reaction (ATR), including allergic reactions, is suspected

following IV/IO infusion of either PRBC or LyoPlas, the transfusion should be stopped immediately. The IV/IO cannula should be retained and the transfusion reaction managed as per standard clinical practice.

9. Pharmacovigilance

9.1 Reporting Requirements

The collection and reporting of Adverse Events (AEs) will be in accordance with the Medicines for Human Use (Clinical Trials) Regulations 2004 and subsequent amendments. The Investigator will assess the seriousness and causality (relatedness) of all applicable AEs experienced by the participant with reference to the reference safety information. This should be documented in the source data.

Standard definitions of different types of AEs are listed in **Table 4a** and categorisation of causality shown in **Table 4b**.

Term	Definition		
Adverse Event (AE)	Any untoward medical occurrence in a patient or clinical trial subject administered a medicinal product and which does not necessarily have a causal relationship with this treatment		
Adverse Reaction (AR)	Any untoward and unintended response in a subject to an investigational medicinal product which is related (or for which a causal relationship cannot be ruled out) to any dose administered to that subject		
Unexpected adverse reaction	 An adverse reaction the nature and severity of which is not consistent with the information about the medicinal product in question set out: (a) in the case of a product with a marketing authorisation, in the summary of product characteristics for that product; (b) in the case of any other investigational medicinal product, in the investigator's brochure relating to the trial in question. 		
Serious adverse event (SAE), serious adverse reaction (SAR) or suspected unexpected serious adverse reaction (SUSAR)	 Any adverse event, adverse reaction or unexpected adverse reaction, respectively, that: results in death; is life-threatening; requires hospitalisation or prolongation of existing hospitalisation; results in persistent or significant disability or incapacity; or consists of a congenital anomaly or birth defect 		
SUSAR	Suspected Unexpected Serious Adverse Reaction (as defined above)		

Table 4a: Definition of standard terms

Table 4b: Categorisation of causality

Category	Definition	
Definitely	There is clear evidence to suggest a causal relationship, and other possible contributing factors can be ruled out	
Probably	There is evidence to suggest a causal relationship, and the influence of other factors is unlikely	
Possibly	There is some evidence to suggest a causal relationship (e.g. the event occurred within a reasonable time after administration of the trial medication). However, the influence of other factors may have contributed to the event (e.g. the participant's clinical condition, other concomitant events)	
Unlikely	There is little evidence to suggest there is a causal relationship (e.g. the event did not occur within a reasonable time after administration of the trial medication). There is another reasonable explanation for the event (e.g. the participant's clinical condition, other concomitant treatments)	
Not related	There is no evidence of any causal relationship	

In the **RePHILL** trial, the LyoPlas and normal saline are categorised as the IMPs and the pharmacovigilance reporting requirements that will be followed are described in this section of the protocol.

As this is a trial using an intervention that also includes a blood component (PRBC), the statutory arrangements for haemovigilance should also be followed (refer to **Section 9.7**).

AEs will be recorded in the medical records as per standard clinical practice. Most (S)AE/ARs that occur in this trial, whether they are serious or not, will be 'expected' treatment-related consequences of the trial intervention or trauma related.

9.2 (Serious) Adverse Events

RePHILL trial participants are likely to have significant co-morbidities and therefore the frequency of AEs is likely to be high. Most of the AEs occurring in **RePHILL**, whether serious or not, will therefore be anticipated in the sense that they are recognised and accepted complications/consequences of major trauma.

Investigators will report AEs that meet the definition of an SAE, other than the SAEs listed in **Section 9.2.1**

9.2.1 Events that do not Require Reporting on a SAE Form

The following are regarded as expected SAEs (i.e. are recognised complications/consequences of major trauma) for the purpose of this trial and should not be reported on an SAE Form. These events should be reported on the appropriate trial CRF(s) instead and will not be subject to expedited reporting.

Event	CRF
Death (from trauma)	Exit Form
Organ failure (single organ)	Daily Assessments
Multi organ dysfunction syndrome	Daily Assessments
Systemic inflammatory response syndrome	Daily Assessments
Acute respiratory distress syndrome	Daily Assessments – Day 7
Infection (any anatomical site)	Daily Assessments
Venous thromboembolism (deep venous thrombosis or pulmonary embolism)	Daily Assessments – Day 7
Transfusion reactions occurring after ED arrival	24 Hour FU and Daily Assessments

SAEs that are related to a pre-existing condition are not required to be reported.

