9.2.3 Reporting Period

Details of all SAEs (except those listed as excluded) will be documented and reported from the date of commencement of protocol defined treatment.

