9.3 Reporting Procedure – Site

9.3.1 Serious Adverse Events

Receiving hospitals should report SAE's which are NOT listed as recognised complications of major trauma (as defined in section 9.2.1), to the **RePHILL** Trial Office on a SAE Form as soon as possible and no later than 24 hours after becoming aware of the event.

Complete SAE Forms should be faxed to the **RePHILL** Trial Office on:

[name] or [name]

The research team at site will be required to respond to any related queries raised by the **RePHILL** Trial Office as soon as possible.

Site Investigators should also notify their own institutions of any SAEs in accordance with their institutional policies.

For SAE Forms completed by someone other than the Investigator, the Investigator will be required to countersign the original SAE Form to confirm agreement with the categorisation of seriousness and causality assessments. The SAE Form should then be returned to the **RePHILL** Trial Office and a copy retained at site.

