9.4 Reporting Procedure – Trial Office

On receipt of the SAE form, the **RePHILL** Trial Office will allocate each SAE a unique reference number which will be forwarded to the receiving hospital as proof of receipt. The SAE reference number should be quoted on all correspondence and follow-up reports regarding the SAE.

On receipt of an SAE Form, seriousness and causality will be reviewed independently by the Chief Investigator (CI; or nominated delegate). A SAE judged to have a reasonable causal relationship with the trial intervention will be regarded as a Serious Adverse Reaction (SAR). The causality assessment given by the PI will not be downgraded by the CI *"or delegate(s)"*. If the CI *"or delegate(s)"* disagrees with the PI's causality assessment, the opinion of both parties will be documented, and where the event requires further reporting, the opinion will be provided with the report.

The CI (or nominated individual will also assess all SARs for expectedness. If the event meets the definition of a SAR that is unexpected (i.e. is not defined in the approved version of the Reference Safety Information) it will be classified as a Suspected Unexpected Serious Adverse Reaction (SUSAR).

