9.7 Haemovigilance

Staff at IDS will be responsible for reporting all transfusion-related adverse events via Serious Hazards Of Transfusion and Serious Adverse Blood Reactions and Events (SHOT/SABRE) according to standard procedures, as required under the regulations of the EU Blood Safety Directive[35, 36]. Similarly, the receiving hospital staff are also responsible for reporting all transfusion-related adverse events, including acute transfusion reactions (<24 hr) and delayed transfusion reactions (>24 hr), to SHOT/SABRE according to standard procedures.

Each individual blood bank issuing blood will have their own their local policies and procedures for the response to a possible transfusion event and should ensure full compliance with their own licence and MHRA. Where the receiving hospital blood bank is different from the issuing hospital blood bank, then both parties should co-ordinate to ensure traceability and reporting.

The hospital blood transfusion laboratory that provided the PRBC (coordinating blood bank) must be informed immediately of all adverse events and reactions. Advice on clinical management and investigation of serious adverse reactions can be obtained from the hospital consultant responsible for blood transfusion at the coordinating blood bank.

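### Section 9.2.1 exempts transfusion reactions by timing, not by causal product, so a serious reaction to trial LyoPlas first seen after ED arrival has no written route to SAR/SUSAR assessment

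*Protocol*

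**What the plan says.** Section 9.2.1 of the protocol tabulates events that sites do not put on an SAE form. It introduces them so: "The following are regarded as expected SAEs (i.e. are recognised complications/consequences of major trauma) for the purpose of this trial". The consequence of being listed is: "These events should be reported on the appropriate trial CRF(s) instead and will not be subject to expedited reporting". One row reads "Transfusion reactions occurring after ED arrival", to be recorded on the 24-hour follow-up and daily assessment forms. The row's only qualifier is time. It does not mention which product caused the reaction, how severe it was or how it ended. The row for death, by contrast, is limited by cause and covers only death from trauma.

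The exclusion is repeated elsewhere. Section 9.2 asks for SAEs other than those in 9.2.1. Section 9.2.3 says "Details of all SAEs (except those listed as excluded) will be documented and reported". Section 9.3.1 asks receiving hospitals for SAEs that are not "listed as recognised complications of major trauma (as defined in section 9.2.1").

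Section 9.4 sets out the central process: "On receipt of an SAE Form, seriousness and causality will be reviewed independently by the Chief Investigator" or a delegate. Next, "A SAE judged to have a reasonable causal relationship with the trial intervention will be regarded as a Serious Adverse Reaction (SAR"). SARs are then judged for expectedness against the approved Reference Safety Information, and those it does not cover become SUSARs. Section 9.5.1 gives 7 days for a fatal or life-threatening SUSAR and 15 days for the others. Section 9.1 names LyoPlas and normal saline as the IMPs. Packed red cells are a blood component for which haemovigilance under 9.7 is also to be followed.

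**The concern.** The trial units are given on scene, before ED arrival, yet a reaction to them can appear later. The protocol accepts this: section 8.4 foresees acute reactions to LyoPlas or red cells, and section 9.7 has receiving hospitals report events "including acute transfusion reactions (<24 hr) and delayed transfusion reactions (>24 hr"). A rule that exempts reactions by the clock therefore catches reactions to the trial product along with reactions to later hospital transfusions, and treats both as consequences of injury.

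At stake is individual-case safety detection for an IMP that section 2.1 describes as not yet tested in an RCT. Section 9.5.1 promises expedited reporting of SUSARs. As written, a site can follow the protocol exactly and a serious in-hospital reaction to LyoPlas need never enter the process that would identify it as one.

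**Working it through.** No arithmetic applies to the rule itself. The check traces cases through section 9 as written.

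**Case A: serious, non-fatal reaction to trial LyoPlas, first seen after ED arrival.**

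1. Section 9.1: the investigator assesses seriousness and causality of all applicable AEs, documented in source data. What counts as applicable is not defined.
2. Section 9.2.1: the event falls in the exempt row by timing. It goes on the 24-hour or daily form and not on an SAE form. Sections 9.2, 9.2.3 and 9.3.1 confirm this.
3. Section 9.4: the Chief Investigator's review is triggered by receipt of an SAE form. None is sent, and no step leads from the 24-hour or daily form into that review.
4. Section 9.4, continued: SAR classification and the expectedness test follow from that review, so neither has a trigger.
5. Section 9.5.1: the 7- and 15-day reports depend on SUSAR classification, so they have no trigger either.
6. Section 9.7: the event still goes to SHOT/SABRE, and the laboratory that supplied the red cells is told at once. Nothing there sends it to the Trial Office or the Chief Investigator.

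**Case B: the same reaction, but fatal.** The death row exempts only death from trauma, so a death from a transfusion reaction can be read as reportable. The transfusion-reaction row is silent on outcome and can be read as exempting the same event. The two rows give different answers.

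**Case C: reaction to trial red cells alone.** Table 4a defines an adverse reaction by reference to an investigational medicinal product, which red cells are not. Section 9.4 defines a SAR by reference to the trial intervention, which includes them. The two definitions disagree.

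**Expectedness, side by side.**

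- Section 9.2.1: expected because the event is a recognised consequence of major trauma, decided in advance from the type of event and when it starts.
- Table 4a: unexpectedness depends on nature and severity against the product information.
- Section 9.4: expectedness is judged against the Reference Safety Information.

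The first standard pre-empts the other two for every reaction in the exempt row.

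**Scale.** Half of the 490 planned participants gives 490 / 2 = 245, the approximate number of plasma recipients stated in section 2.4. The protocol gives no rate of transfusion reactions, so no expected count follows.

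**The case against.** Several points on the other side stand.

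- **Causality is still assessed locally.** A reader might infer that these reactions escape causality review altogether. They do not: section 9.1 keeps the investigator's assessment. What lacks a trigger is the independent central review.
- **Nothing forbids the classification.** A reader might infer that such reactions cannot become SARs or SUSARs. No sentence says so. What the protocol lacks is a written route, and for fatal reactions the death row arguably supplies one.
- **Red cells.** They are not an IMP and are directed to haemovigilance, so the gap should not be stated for them in the same terms as for LyoPlas.
- **ARDS.** It is also in the 9.2.1 table, and secondary objective VII names it, so a reader might want it on SAE forms too. But major trauma is itself treated as a cause of ARDS here, and the trial records ARDS on CRFs as a secondary outcome compared between arms. That is a defensible choice.
- **Share of the reaction window.** A reader might express the exempt period as a share of the first 24 hours. That would be a share of clock time, not of reactions. It also needs a time from first unit to ED that the protocol does not give. The 1-hour subgroup cut in 11.2.3 runs from injury, and section 7.1.2 provides for participants still on scene 2 hours after randomisation.
- **How many expedited reports are lost is unknown.** The Reference Safety Information is not shown. Reactions it lists would be expected and would not be SUSARs whichever form was used.

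The remaining safeguards are real, but they do not close the gap. SHOT/SABRE and blood-bank notices do not reach the Trial Office. The site assessment stays in source data. The report under 9.5.2 is annual and the DMEC meets at least annually. Immediate notification under 9.5.3 presupposes that a significant issue has already been identified.

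**Conclusion.** The point holds in a limited form. Section 9.2.1 exempts transfusion reactions after ED arrival by timing and not by causal product, and its reason for calling them expected conflicts with Table 4a and section 9.4. For a serious, non-fatal reaction to trial LyoPlas first seen in hospital, the protocol has no written path to independent review, SAR/SUSAR classification or the 7- and 15-day reports. For fatal reactions the table is ambiguous, and for red cells the definitions are inconsistent.

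The population exposed is about 245 participants. The number of reactions affected cannot be derived from the document. The trial's treatment-effect estimates are not affected. The conclusion assumes that section 9 is applied as written and that no separate safety procedure, not shown here, routes CRF-recorded reactions to the Chief Investigator. Because the rule produces the wrong result for an IMP and is cheap to correct, it should be corrected.

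**What to change.** 1. In 9.2.1, limit the transfusion-reaction row to reactions after ED arrival judged not related to a trial IMP. State that any serious reaction, at any time, for which a causal relationship to trial LyoPlas cannot be ruled out goes on an SAE form within the 24 hours already set in 9.3.1 and is assessed under 9.4 and 9.5.
2. Mirror that exception in 9.2.3 and 9.3.1.
3. Reconcile the row with the death row, so that it is clear how a death from a transfusion reaction is reported.
4. Reconcile the wording of 9.4, which refers to the trial intervention, with the IMP-based definition in Table 4a. State whether a reaction to trial red cells alone is handled by haemovigilance only or also under 9.4.

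The cost is a short protocol amendment and a few more SAE forms. Reactions judged unrelated to a trial IMP, including those due only to later hospital transfusions, stay on the CRFs, so the exemption still does most of its work. No change to the ARDS row is needed.

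### The reporting waiver for SAEs related to a pre-existing condition has no exception for events that the trial product may also have caused, so suspected serious reactions can bypass central causality and SUSAR review

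*Protocol*

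**What the plan says.** Section 9.2 of the protocol sets the general duty: "Investigators will report AEs that meet the definition of an SAE, other than the SAEs listed in" section 9.2.1. That section tabulates expected consequences of major trauma, such as organ failure, infection and venous thromboembolism. It gives each a CRF to be used in place of the SAE Form. After the table comes one free-standing sentence: "SAEs that are related to a pre-existing condition are not required to be reported". It names no alternative CRF and sets no condition on relatedness to the trial intervention.

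Section 9.2.3 repeats the general rule: "Details of all SAEs (except those listed as excluded) will be documented and reported from the date of commencement of protocol defined treatment". Section 9.3.1 asks receiving hospitals for an SAE Form within 24 hours for SAEs that are not "listed as recognised complications of major trauma (as defined in section 9.2.1".

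On causality, Table 4a in section 9.1 defines an adverse reaction as a response "which is related (or for which a causal relationship cannot be ruled out) to any dose administered to that subject". Table 4b describes *Possibly* as some evidence of a causal link, and adds: "However, the influence of other factors may have contributed to the event (e.g. the participant's clinical condition, other concomitant events". On central review, section 9.4 states: "On receipt of an SAE Form, seriousness and causality will be reviewed independently by the Chief Investigator".

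**The concern.** The waiver treats a link to a pre-existing condition as if it settled causality. The protocol's own definitions do not. A participant's earlier illness and the trial fluid can both contribute to one event, and Table 4b provides for that.

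Central safety review is at stake. Section 9.4 is where a site report becomes a SAR and, if unexpected, a SUSAR. SUSARs then go to the regulator and ethics committee within 7 or 15 days (9.5.1), and SAEs and SARs enter the annual safety report (9.5.2). An event with no form has no stated way into that sequence. The affected group is not marginal, since section 9.2 says that "participants are likely to have significant co-morbidities". Because SUSAR reporting acts on single events, one missed case would count.

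**Working it through.** No arithmetic applies. The check sets the sections side by side.

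1. **Can one event be related to a pre-existing condition and also be a suspected reaction?** Yes. Table 4a needs only that a causal link to the product cannot be excluded. Under *Possibly*, Table 4b names the participant's clinical condition as a factor that may have contributed as well. The two attributions can coexist.

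2. **Does the waiver separate such events from purely background ones?** No. Section 9.2.1 does not mention the trial intervention, Table 4b or the Investigator's causality judgement. Take, as an illustration, a myocardial infarction after the trial boluses in a participant with known coronary disease. It is not named in the trauma table. If the Investigator graded it *Possibly*, it would be a suspected serious reaction under 9.1 and waived under 9.2.1.

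3. **What happens without a form?** The Chief Investigator's causality review in 9.4 is triggered by receipt of an SAE Form, and expectedness is assessed only for events already classed as SARs. Section 9.4 also bars the Chief Investigator from downgrading the site's causality grade. That protection has no effect on an event that is not submitted.

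4. **Are there other routes?**
   - Section 9.1 has the Investigator assess causality of all applicable AEs in the source data. The protocol does not say which AEs are applicable, and no step carries the assessment to the Trial Office without a form.
   - Section 9.7 sends transfusion-related adverse events to SHOT/SABRE and the coordinating blood bank. It does not mention the Trial Office, the Chief Investigator or SUSAR classification, and section 9.1 presents haemovigilance as an additional requirement. It does not cover normal saline, which sections 8.1.2 and 9.1 class as an IMP.
   - Daily Assessments, SOFA scores, the Exit Form and the transfusion-complication outcome record some of these events as data. None is stated to start the review in 9.4.

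5. **Do the reporting sections agree?** No. Section 9.3.1 exempts only the listed trauma complications, and an SAE related to a pre-existing condition is not among them. Read literally, 9.3.1 requires a form where 9.2.1 waives it. Sections 9.2 and 9.2.3 refer to listed exclusions and leave unclear whether the free-standing sentence counts as part of the list.

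**The case against.** The best defence is that the sentence means something narrower. Table 4b also mentions the participant's clinical condition under *Unlikely*, as another reasonable explanation for the event. A site could therefore take the waiver to cover only events attributed to the earlier illness instead of the product. That reading is plausible and may be what was intended, but the text does not say so, and a site that follows the words can waive a *Possibly* event.

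Three stronger readings are tempting, and the documents do not support them.

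- A reader might infer that sites are told to withhold these events. The waiver is permissive. It contrasts with the tabulated trauma events, which are to be kept off the SAE Form, and 9.3.1 read literally asks for a report.
- A reader might infer that serious reactions in comorbid participants never reach causality review or trial data. Site assessment continues under 9.1, SHOT/SABRE receives transfusion-related events, and several CRFs record organ failure, infection, thromboembolism and death. The waiver covers only SAEs related to the pre-existing condition, not every reaction in a participant who has one.
- A reader might multiply the roughly 245 plasma recipients mentioned in section 2.4 by assumed rates to obtain a count of lost reactions. The protocol gives neither a comorbidity rate nor a rate of product-related events, so any such count would rest on invention.

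These points narrow the concern but do not remove it. Optional reporting of suspected serious reactions, decided site by site in an open-label trial, is a weak substitute for a rule.

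**Conclusion.** The point holds in a limited form. As written, section 9.2.1 lets an SAE that is related to a pre-existing condition and possibly also to the trial product bypass the Chief Investigator's causality review and SUSAR classification. It also contradicts section 9.3.1. The other routes are partial safeguards, weakest for normal saline and for events outside the tabulated categories.

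The size cannot be stated as a number. The conclusion rests on the wording of 9.1, 9.2.1, 9.3.1 and 9.4, and on the assumption that some sites would apply the waiver literally. This is a stated rule that conflicts with the protocol's own definitions, not a detail left for the SAP. It should be corrected.

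**What to change.** Make three linked wording changes.

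- **Section 9.2.1:** limit the waiver to SAEs related to a pre-existing condition that the Investigator judges *Not related* or *Unlikely* to be related to the trial intervention. State that those judged *Possibly*, *Probably* or *Definitely* related are reported under 9.3.1 within its existing 24-hour limit.
- **Section 9.3.1:** describe its exemptions in the same terms, so that the trauma list and the limited waiver are both named and nothing else is exempt.
- **Sections 9.2 and 9.2.3:** point to the same set of exemptions.

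The cost is a short protocol change, a line in site training and a few extra SAE Forms. The relatedness judgement stays with the site Investigator, where section 9.1 already places it, so the change does not add an independent look at events graded unrelated. It does ensure that a suspected reaction is not exempted because another cause is also present.
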